1.3.7 Study Interventions and Adherence

At enrollment into Look AHEAD, participants were randomized within center on a 1:1 basis to the ILI or DSE conditions. The ILI included diet modification and physical activity and was designed to achieve and maintain weight loss of at least 7% (Wadden, 2006). ILI participants were assigned a caloric goal of 1200 – 1800 kcals/day based on their initial weight, with < 30% of total calories from fat and a minimum of 15% of total calories from protein. The physical activity goal was ≥ 175 minutes of unsupervised moderately intense physical activity per week and focused on activities similar in intensity to brisk walking. ILI participants were seen weekly for the first 6 months and three times per month for the next 6 months, with a combination of group and individual sessions. During years 2-4, participants were seen individually at least once per month and had a minimum of one additional contact by phone, mail, or email per month. During Year 5+, participants were encouraged to continue individual monthly sessions and annual campaigns were used to promote adherence. A tool kit of strategies was available for ILI participants having difficulty achieving the weight loss goals.

DSE participants were invited to three group sessions focused on diet, physical activity, or social support each year for the first 4 years and one session annually thereafter.

All interventions were terminated in September, 2012, as instructed by NIDDK based on the recommendation of the DSMB. For intention-to-treat analyses of the potential legacy effects of ILI on Look AHEAD Extension outcomes, participants will be categorized according to their original randomization assignments.

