Frailty is the primary outcome for this aim and is a new aim because it has not been measured prior to LA-E. It will be assessed using the Fried criteria [Fried, 2001] developed during the Cardiovascular Health Study. Frailty classification is based on the presence of five frailty characteristics: 1) walking speed standardized based on median height and sex, 2) grip strength standardized based on body mass index (BMI) and sex, 3) energy expenditure standardized based on sex, 4) exhaustion based on self-report, and 5) weight loss of 10 lbs or more in the last year without trying or intending to (based on self-report). Walking speed will be assessed using the timed short walk included in the Short Physical Performance Battery (SPPB) and grip strength. Energy expenditure will be based on kcal/week of energy derived from the Paffenbarger physical activity questionnaire. Exhaustion will be assessed using the question from the Geriatric Depression Scale, "Do you feel full of energy?." Weight loss will be assessed by self-report. (We acknowledge that this is a difficult item to interpret for the LA cohort, and will also examine the impact on a construct without this item.) Based on these assessments, frailty will be classified into three stages: non-frail (no frailty characteristics present), pre-frail (1 or 2 frailty characteristics present), and frail (3 or more frailty characteristics present). Our primary analysis will classify a person as having prevalent frailty if they are classified as frail during either of the LA-E visits. The proportion of participants experiencing any frailty will be compared between randomized groups using logistic regression, with clinic site, sex, and time from randomization to classification of frailty or the last non-frail classification as covariates. Odds ratios and 95% confidence intervals will be used to summarize the relative effect of the intervention on frailty.

Supporting analyses: include persistent major mobility disability (PMMD) based on repeated assessments of the adjudicated 400-m walk, sensitivity analyses for frailty and PMMD, falls, fractures, SPPB, grip strength, and Pepper Assessment Tool for Disability (PAT-D).

PMMD is considered present when an individual fails to complete two successive 400-m walks [Newman, 2006; Pahor, 2014]. Death after an initial MMD determination will also be considered

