Power: We used the distribution of expected follow-up times and longitudinal sequences of SF-36 scores to project the standard error that would be available to detect mean differences between intervention groups on post-intervention SF-36 scores (i.e. difference from baseline), arriving an estimate of 0.027 SD units. This provides 90% power to detect an overall mean difference of 0.088 SD units. At year 10 during the intervention phase, the mean difference was 0.106, thus we project >90% power to detect a difference over time even if it wanes post-intervention.

5.6 Specific Aim 6 (tertiary) is to describe the long-term trajectories of a) weight, b) physical activity, c) fat and lean mass, and d) bone density within and between the intervention groups and examine how these are related to outcomes, including those defined by the primary and secondary aims.

Weight change has been monitored annually throughout the study. We will summarize the patterns of weight loss and regain using both continuous measures [e.g. Espeland, 2009; Neiberg, 2012] and categorical measures with clinically meaningful cutoffs. **Body composition and bone density** will be assessed objectively using **dual X-ray absorptiometry**. This will be collected at the first clinic visit in LA-E on all participants who have previous measurements at baseline and one or more post baseline time points (a total of approximately 800 participants from 5 sites). We will calculate change in total and regional (e.g., arm, leg, and trunk) fat mass and lean mass. We will also calculate change in whole body and regional (e.g., hip, arm, leg, trunk, spine, pelvis) bone mineral content (BMC) and bone mineral density (BMD). Longitudinal trajectories for the continuous outcomes between DSE and ILI will be compared using linear mixed effects models. Ordinal outcomes (e.g., weight change categories) will be compared

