using generalized linear models with a cumulative logit link function and a binomial error term. **Physical activity** will be assessed objectively using **accelerometry** on a subset of participants. This will be collected at the first clinic visit on all LA-E participants who have previous measurements (from substudies at years 0, 1, 4 at the Baltimore, Baton Rouge, Denver, Houston, Memphis, Minneapolis, Philadelphia, and Providence sites and years 8 and 10 at the Pittsburgh site). The total sample size for this sub-study will be approximately 1,800 individuals. We note that the RT3 accelerometer was used in LA. However, this technology is outdated. LA-E will use an alternative device (wrist actigraph), which provides 24-hr physical activity and sleep information. A cross-validation study will be conducted to allow us to compare the RT3 and the wrist actigraph prior to implementation study-wide. This will allow for the development of a calibration factor to be established in the event that there are differences in the activity counts between the two devices. Summary scores for the accelerometry data will be based on recommendations from the American College of Sports Medicine and the American Heart Association [Haskell, 2007]. Moderate intensity physical activity will be defined as ≥ 3 METs per minute, where METs per minute is metabolic equivalents (METs) per minute and will be obtained by dividing the estimated total energy expenditure per minute by the estimated resting energy expenditure. Vigorous intensity physical activity will be defined as ≥ 6 METs per minute. Bouts of activity will be defined as ≥ 10 minutes in duration. Summary measures include (but not limited to) bouts per day, minutes per bout, METs per minute, and total METs for moderate/vigorous physical activity will be compared between DSE and ILI using linear mixed effect models. Data from the accelerometry will also be used to determine time spent in sedentary activities (< 1.5 METs per minute) and sleep. All these measures will be considered as potential mediators and used in mediation analyses. Physical activity will also be assessed with the **Paffenbarger** questionnaire on all participants. We will use linear mixed effects models to compare longitudinal trends between intervention groups.

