Use of mediation analytical techniques in a randomized trial setting has traditionally required the assumption that the mediation factor is randomly assigned to individuals (i.e., the sequential ignorability assumption), making such analyses unprotected from unmeasured confounders, which can lead to biased inferences [Lynch, 2008]. Two approaches that have been proposed to investigate causal mediation in a randomized trial context are structural mean models [Robins, 1994; Ten Have, 2004; Ten Have, 2007] and principal stratification [Frangakis, 2004; Frangakis, 2002]. More recently, Imai, Tingley and colleagues provided an R package (mediation) to allow design-based mediation inference (i.e. it does not require the sequential ignorability assumption) in a wide variety of settings, including allowing for multiple mediators [Imai, 2013ab; Tingley, 2014]. To explore the hypotheses under this aim, we will determine how approaches within these families of causal mediation models can be used to assess how post-randomization levels of body composition, bone density, physical activity and weight may account for the indirect effects of the intervention on outcomes (including PMMD and frailty) within the framework of the models used to measure the direct effect of the intervention on these outcomes.

Supporting analyses: LA provides many other measures that may inform mediation analyses, including trajectories of physical function, waist circumference, CVD risk factors, and medication use. We will also examine how events (e.g. fractures) influence subsequent outcomes.

5.7 Additional Analyses.

The rich LA databases offer the opportunity to explore many additional analyses. Data on genetics, cognitive function, medications, and many biomarkers are available to examine

associations these have with LA-E outcomes. A range of modelling approaches will be used to describe longitudinal trajectories of measures and to compare these between intervention groups. We are interested in examining whether there are patterns of responses and will use multivariate approaches to describe clusters of responses. As noted above, we are experienced with using latent variable approaches such as hidden Markov modeling to assist with this. The prevalence of cognitive impairment will be assessed using logistic regression and the incidence rates from the Look AHEAD Continuation to the Extension will be computed.

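### The exploratory mediation analysis (SAP 5.6) credits a package with avoiding sequential ignorability, which one randomization cannot do, and has no rule on mediator timing or overlap with the frailty score.

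*Combined protocol and SAP*

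**What the plan says.** **Method.** SAP 5.6 opens its mediation paragraph with a warning: traditional methods treat the mediator as if randomly assigned, "making such analyses unprotected from unmeasured confounders, which can lead to biased inferences". It then names structural mean models, principal stratification and an R package credited with "design-based mediation inference (i.e. it does not require the sequential ignorability assumption) in a wide variety of settings". No method is chosen: "we will determine how approaches within these families of causal mediation models can be used to assess" the question.

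**Mediators and outcomes.** The aim is to see how post-randomization body composition, bone density, "physical activity and weight may account for the indirect effects of the intervention on outcomes (including PMMD and frailty"). No visit is fixed for the mediator. For the accelerometry summaries SAP 5.6 is firmer: "All these measures will be considered as potential mediators and used in mediation analyses".

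**Timing.** In LA-E, DXA is done once: "This will be collected at the first clinic visit in LA-E on all participants who have previous measurements at baseline" and at a later point. Accelerometry is also taken at exam 1 only (protocol Table 1; SAP Exhibit 1). SAP 5.3 counts a person as frail if classified so at either LA-E exam. It builds PMMD from one LA-C walk and two LA-E walks, with onset at the initial failure.

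**Content of the frailty score.** Two of the five criteria in SAP 5.3 are low energy expenditure and unintended loss of 10 lb or more in a year. For the former, "Energy expenditure will be based on kcal/week of energy derived from the Paffenbarger physical activity questionnaire". Grip strength is also standardized by BMI.

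**Randomization.** Protocol 1.3.7: "participants were randomized within center on a 1:1 basis to the ILI or DSE conditions".

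**The concern.** Three separate features could each make a mediator look as though it carries the intervention effect when it does not.

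1. **Identification.** Readers are told that one of the methods on offer needs no assumption about mediator-outcome confounding. If an indirect effect is reported on that footing, its main source of bias goes unstated.
2. **Order.** Frailty or mobility loss can itself lower activity and lean mass. If the mediator is measured at or after onset, that reverse path is counted as mediation.
3. **Overlap.** A measure that is also a component of the outcome score is associated with the outcome by construction.

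What is at stake is the answer to a stated tertiary aim: how these measures relate to the primary and secondary outcomes. The randomized comparisons of ILI with DSE are not at stake.

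**Working it through.** **1. What the design identifies.** Let A be arm, M mediator and Y outcome. Randomizing A identifies E[Y | A=1] − E[Y | A=0] and the effect of A on M. An indirect effect needs the mean of Y under one arm with M at the level it would take under the other. No participant is observed in that state. A second randomization, of M or of encouragement to change M, could help, but the documents describe none. With A alone randomized, an assumption linking M and Y is still required. Structural mean models and principal stratification replace sequential ignorability with other assumptions, and SAP 5.6 states none. The sensitivity analyses in SAP 4.4 and 5.3 concern missing data, case definitions and state transitions, not mediator-outcome confounding.

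**2. Timing, set side by side.**

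| Outcome | When it can first be recorded | Relation to exam 1 DXA or accelerometry |
|---|---|---|
| Frailty | Exam 1 | Same exam |
| Frailty | Exam 2 | About two years later |
| PMMD | Initial failure at LA-C walk | Onset precedes the mediator |
| PMMD | Initial failure at exam 1 | Same exam |
| PMMD | Initial failure at exam 2 | Onset recorded later |

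The plan does not restrict exam 1 mediators to the two rows where the outcome follows.

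**3. Plan figures, for context.** The mediation analysis has no sample size or power statement. For its two named outcomes, ILI rate = p·OR/(1 − p + p·OR):

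- Frailty: 0.08 × 0.70 / (0.92 + 0.056) = 5.74%. Power with 1,900 per arm is 78.7%.
- PMMD: 0.127 × 0.75 / (0.873 + 0.09525) = 9.84%. Power is 79.7%.

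Both agree with the stated 80% to within two points. At the same rates the accelerometry substudy (1,800) would hold 900 × 0.08 + 900 × 0.0574 ≈ 124 frail cases, and the DXA substudy (800) about 55. Power for the total frailty effect would be 47.5% and 24.3%.

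**4. How often false mediation appears.** Simulation, 1,000 runs per cell. Assumptions that are not in the documents: arm shifts the mediator by 0.15 to 0.25 SD, and frailty is about 7%. Mediation is declared when both the arm-to-mediator path and the mediator-to-outcome path (given arm) have |z| > 1.96.

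| Situation | N = 1,800 | N = 3,800 | Mean indirect effect, percentage points |
|---|---|---|---|
| No confounding, true indirect effect zero | 4–5% | 4–5% | 0 |
| Unmeasured common cause, mediator-liability correlation 0.1–0.3 in size, true effect zero | 54–100% | 89–100% | 0.2–1.0 |
| Frailty lowers same-exam mediator by 0.3–0.6 SD, true effect zero | 79–100% | 99–100% | 0.3–0.9 |
| Mediator is one of five frailty items, no other link | 87–99% | 99–100% | 0.4–0.7 |

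In the last row the indirect effect equals the whole total effect, by definition only. For scale, the plan's assumed total frailty effect is 8.0 − 5.74 = 2.26 points, so 0.2 to 1.0 points is roughly 9% to 44% of it.

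**5. How large a share could be spurious.** Second model: ILI raises an underlying vigor trait by 0.2 SD, five items load 0.5 or 0.7 on it, comparator frailty is about 11%, the odds ratio is about 0.7 to 0.75, and activity has no causal effect. Share mediated = 1 − direct/total.

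| Mediator and frailty score | Spurious share |
|---|---|
| Same-visit activity item, full score | 39–60% |
| Same item, activity item dropped from score | 25–49% |
| Separate device correlated 0.5 with the item, full score | 10–15% |
| Separate device, item dropped | 6–13% |
| Earlier activity value (trait correlation over time 0.7–0.9), item dropped | 17–44% |

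The last row shows that earlier measurement and a trimmed score do not remove a common cause.

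**The case against.** The strongest reply is that SAP 5.6 is exploratory, serves a tertiary aim, opens by warning about unmeasured confounders, and lists the package as one option among several. That stands. A reader might infer that the plan commits to an assumption-free method; it does not. The parenthesis is still wrong for this design, and no identifying assumption is given for any option.

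A reader might also infer that every mediator is measured at the same exam as the outcome. The documents do not support this. SAP 5.6 speaks of post-randomization levels generally. Weight was recorded annually, earlier DXA and RT3 values exist, and all participants completed the Paffenbarger questionnaire at year 8 (protocol 1.4.3). First frailty at exam 2 follows the exam 1 mediators. What is missing is a rule requiring that order.

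The overlap is limited to frailty. It does not reach PMMD, mortality, costs or end-stage renal disease. Accelerometry and DXA are different instruments from the frailty items, and the weight criterion is self-reported unintended loss, not weight level. SAP 5.3 already plans a frailty construct without the weight item, though it is not tied to mediation and there is no version without the activity item.

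Extending the timing point to deaths before exam 1 is tempting. The mediation paragraph names only PMMD and frailty, and the documents give no figure for the share of deaths before exam 1, so no size is claimed for mortality.

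**Conclusion.** The point holds for the tertiary mediation analysis. The claim that sequential ignorability is not required does not fit a trial with one randomization and no randomized mediator. The plan permits exam 1 mediators for outcomes found at or before exam 1, and permits activity and weight as mediators of a frailty score that partly contains them.

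These features can yield apparent mediation where none exists. A reader might infer that false mediation will be reported. That goes too far, because the result depends on the method and mediator values chosen and on the strength of confounding. The simulated rates and shares rest on assumed path sizes, correlations and loadings. The 39–60% share in particular applies when the mediator is the frailty item itself, and it falls to 10–15% for a separate device under the stated correlation. No primary or secondary test is affected.

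**What to change.** In SAP 5.6:

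1. Delete or qualify the statement on sequential ignorability. State the identifying assumption of the method used, and report each indirect effect with a sensitivity analysis for unmeasured mediator-outcome confounding.
2. Use mediator values measured before the outcome. Take earlier post-randomization values where they exist for that mediator: annual weight, earlier DXA and RT3, year 8 Paffenbarger. Use exam 1 values only for outcomes first arising after exam 1, which means excluding people frail at exam 1, or with an MMD failure at or before exam 1, from the corresponding model.
3. When activity or weight is a mediator of frailty, score frailty without the activity and weight-loss items.

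Steps 2 and 3 reduce reverse causation and overlap but leave common-cause confounding, so step 1 is needed as well.

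**Cost.** SAP wording and re-specified models on data already held or already scheduled. The downside is fewer usable events and wider intervals, in substudies that would hold only about 124 and 55 frail cases before any exclusion. Earlier accelerometry is also limited: years 0, 1 and 4 at eight sites, where year 0 precedes the intervention and can serve only as a covariate, and years 8 and 10 at one site.
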